### 11.2 Populations for Analysis

The safety population consists of all subjects enrolled.

The primary analysis population will be the Full Analysis Set (FAS). The FAS is defined as all randomized subjects.

The per protocol population (PP) consists of all subjects who have completed all visits according to the protocol. Detailed criteria for assignment to the PP population will be described in the SAP.

### **11.3 Handling of subject withdrawals and missing values**

As described in 11.2, all randomized subjects will be part of the FAS group and thus be utilized for primary analysis. The pink (left) part of the DTQ will be assessed before randomization. This will guarantee that no bias will be introduced by a possible preference of subjects for a particular group, resulting in a possible withdrawal of individual subjects right after randomization.

For subjects that answered DTQ during Visit 4, these answers will be used for the primary analysis.

The following steps are planned to avoid missing data:

- In case of withdrawal, subjects will be asked to answer the DTQ questionnaire during the End of Study visit.
- If it will not be possible to get questionnaire results at the End of Study visit but questionnaire results are available from week 13 (visit 3), these results will be used, i.e. a LOCF procedure will be applied.
- If there will be no results from week 13, e.g. because a subject will withdraw before week 13, a value of 3 (“Same”) will be imputed as the answer to every individual question. This will result in a total score of 90 (30 times 3), which corresponds to the assumed mean result for the MDI group and thus represents a conservative imputation (the anticipated mean score for the Accu-Chek® Solo group is 110).

### **11.4 Missing values for scores other than the primary endpoint will be imputed using a LOCF approach, where applicable. Details will be specified in the SAP. Subject Demographics and Baseline Characteristics**

The following demographic and baseline characteristics will be summarized by study group:

- Gender, age and race.
- Height, weight, body mass index, blood pressure and pulse rate.
- Handedness.
- Highest level of education.
- Current employment status and family status.
- Diabetes Background and History
- Diabetes Medication.
- Baseline HbA1c.
- Medical History - diseases other than Diabetes
- Previous Medications for diseases other than Diabetes.

All subject characteristic variables will be summarized descriptively. Continuous variables will be summarized in terms of descriptive statistics including the number of subjects (N) without missing values, mean, median, standard deviation, and range

Categorical variables will be summarized in terms of absolute frequencies and percentages. In general, the denominator for the percentage calculation will be based upon the total number of subjects in the study population, unless otherwise specified.

### 11.5 Primary Objective Analysis

The primary objective of this study is to assess the change in treatment satisfaction between start of study and the end of its parallel phase. Change in treatment satisfaction will be assessed by the change in answers to the questions of the Diabetes Technology Questionnaire (DTQ). These answers range from “Much worse” (score 1) over “Same” (score 3) to “Much better” (score 5). In the MDI group, participation in this study results in no treatment change and therefore the mean anticipated score per question is 3, while a significantly higher score is anticipated for the Solo group.

The primary analysis consists of two individual comparisons, firstly the comparison between the between the Accu-Chek® Solo and MDI and secondly between Accu-Chek® Solo and mylife™ OmniPod®. The two comparisons will be performed using a hierarchical procedure.

First, the results from the Accu-Chek® Solo group will be compared to those of the MDI group. Only if the Null hypothesis of no difference in treatment satisfaction between Accu-Chek® Solo and MDI can be rejected, Accu-Chek® Solo will also be compared to mylife™ OmniPod®.

The comparisons will be performed using an ANCOVA with the DTQ score as dependent variable and treatment arm, baseline DTQ score, and site as covariates.

Details of the statistical analyses will be described in the SAP.

### 11.6 Secondary Objective(s) Analysis

For subjects from groups B (starting with MDI) and C (starting with mylife™ OmniPod®), who will all use the Accu-Chek® Solo micropump after week 26, the change in DTQ score between week 26 and week 39 will be analyzed.

Additionally, the following parameters will be tested. More parameters may be specified in the statistical analysis plan (SAP). Both pairwise tests (Accu-Chek® Solo versus MDI and Accu-Chek® Solo versus mylife™ OmniPod®) and simultaneous analyses of all three treatment alternatives will be performed where applicable, e.g. using an Ancova with treatment arm as independent variable. Baseline adjustment will be performed where applicable. Details will be specified in the SAP.

- Psychological parameters that describe or affect therapy:
  - Treatment satisfaction with Accu-Chek® Solo system vs. mylife™ OmniPod®, measured by the difference in the Diabetes Technology Questionnaire (DTQ) change score after 26 weeks.
  - Diabetes-related Emotional Distress assessed by PAID-5.
  - Device satisfaction
  - Device and Treatment Preference
- Physical parameters that describe therapy changes or success:
  - HbA1c
  - Change in weight and BMI
  - Glycemic variability
- Therapy parameters that describe therapy changes or may affect the results
  - Indication for commencement of CSII
  - Type of insulin used
  - Total daily insulin dose (TDD)

- Total daily basal insulin dose (TBD)
- Average number of SMBGs per day
- Frequency of hypoglycemic events
- Frequency of hyperglycemia
- Frequency of consultations between scheduled visits, emergency and call center calls, hospitalizations and absenteeism from work/school
- Device specific parameters that may affect user acceptance
  - Number of pods/ infusion assemblies falling off prematurely
  - Average infusion assembly usage time
  - Number, type and intensity of skin reactions
- Parameters that may affect socio-economic acceptance
  - Insulin amount left in device at reservoir change / device discard
  - Amount of waste, inferred by total material consumption
- Subject withdrawal
  - It will be tested whether there is a bias in the fraction of subject withdrawal among the different treatment arms
- Descriptive evaluation:
  - Accu-Chek® Solo micropump system: Training Satisfaction

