### 11.1 Null Hypotheses and Sample Size Calculation

Assessment of treatment satisfaction in patients with type 1 diabetes comparing standard therapy via MDI to patch pumps.

First Null hypothesis: There is no difference in treatment satisfaction between Accu-Chek® Solo and MDI.

First Alternative hypothesis: Treatment satisfaction is higher with Accu-Chek® Solo than with MDI.

Second Null hypothesis: There is no difference in treatment satisfaction between Accu-Chek® Solo and mylife™ OmniPod.

Second Alternative hypothesis: Treatment satisfaction is higher with Accu-Chek® Solo than with mylife™ OmniPod.

The first and second Null hypothesis are tested using a hierarchical procedure. Only if the first Null hypothesis of no difference in treatment satisfaction between Accu-Chek® Solo and MDI can be rejected, the second Null hypothesis of no difference in treatment satisfaction between Accu-Chek® Solo and mylife™ OmniPod will also be tested.

Sample size calculation is based on the expected difference and variability in the DTQ change score between the Accu-Chek® Solo and the MDI group. An anticipated mean score of 90 in the MDI group and of 110 in the Solo group and a standard deviation of 30 is used for sample size calculation.

A sample size of 49 subjects per group will have a 90% power to detect a significant difference at a two sided alpha level of 0.05. To adjust for a maximum drop-out rate of up to 18%, 60 subjects will be enrolled in every treatment arm.

To allow for comparison between the Accu-Chek® Solo and the mylife™ OmniPod, the same number of subjects as in groups A and B will be enrolled in group C. No assumptions on the difference in change of treatment satisfaction between the Accu-Chek® Solo and in the mylife™ OmniPod groups are made and thus, sample size is not adjusted for this comparison. Also, since testing of the first and the second Null hypothesis will be performed using a hierarchical procedure, no multiplicity correction and thus no sample size adjustment is necessary.

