## 2.2. Study Design

This study is conducted as a prospective, multinational, multicenter, three-arm study where adults with type 1 diabetes will be enrolled in approximately 20 sites.

A total of 180 subjects will be randomly allocated in a 1:1:1 ratio to the three treatment groups.

Due to the character of the used devices, no blinding procedure will be utilized.

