#### **6.8.1.1. DTQ**

For DTQ both the change scores and the status scores will be analyzed. For the change scores, the same ANCOVA as for the primary analysis will be used. All other comparisons will be analyzed using t-tests.

Difference scores as described in section 6.8.1 will be performed both on the “now” scores and on the “change” scores, even though the latter ones already reflect differences/changes.

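### Solo vs OmniPod on the week-26 DTQ change score is a gated primary test, but Protocol 11.6 lists it again as a secondary test without the gate, and the SAP does not clearly close the gap

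*Protocol*

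**What the plan says.** **The gate.** Protocol 4.1, 11.1 and 11.5 set a fixed sequence: Solo vs MDI (H1) first, then Solo vs OmniPod (H2) only if H1 is rejected. Protocol 11.5 states: "The two comparisons will be performed using a hierarchical procedure". SAP 2.7 and 6.6 repeat the condition. Protocol 11.1 relies on this sequence to conclude that "no multiplicity correction and thus no sample size adjustment is necessary", and SAP 2.8 says the same.

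**The duplicate.** Protocol 11.6 introduces its list as parameters to be tested in addition, with pairwise tests that include Solo vs OmniPod. The first bullet under psychological parameters is treatment satisfaction with Solo vs OmniPod, "measured by the difference in the Diabetes Technology Questionnaire (DTQ) change score after 26 weeks". Those quoted words also appear in the gated primary objective in Protocol 4.1. What differs in 11.6 is the setting: a list of secondary tests, with no condition on H1.

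**The SAP's secondary DTQ analysis.** SAP 6.8 covers secondary endpoints by arm and visit, and 6.8.1 includes Visit 4 among the visits. SAP 6.8.1.1 then says: "For the change scores, the same ANCOVA as for the primary analysis will be used". It mentions no gate. SAP 6.8.1.2, on HbA1c, does refer back to the hierarchical order of section 2.7.

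**The concern.** The bullet in Protocol 11.6 has the same arms, score and time point as H2. Under 11.5 the comparison is not made if H1 is not rejected; under 11.6 it is tested regardless. An analyst working from SAP 6.6 would withhold the p-value, and one working from 6.8.1.1 could reasonably produce it.

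The order of testing is the only device that protects the 5% level across the two comparisons. Neither document says whether secondary tests are confirmatory or exploratory, or how a Solo vs OmniPod p-value should be treated if H1 is not rejected. Protocol 3.2.2 describes OmniPod as the only patch pump on the market, so there would be interest in reporting this comparison even if Solo vs MDI failed.

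**Working it through.** **1. Reproduce the plan's sample size.** Protocol 11.1 gives "An anticipated mean score of 90 in the MDI group and of 110 in the Solo group and a standard deviation of 30", and concludes that "49 subjects per group will have a 90% power to detect a significant difference at a two sided alpha level of 0.05".
- Normal approximation: n = 2 × (1.960 + 1.282)² × (30/20)² = 2 × 10.51 × 2.25 = 47.3, so 48 per group.
- The exact two-sample t calculation gives 49 per group, with power 90.4%.
- Drop-out: 49 / (1 − 0.18) = 59.8, so 60 per arm.

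Both stated figures are reproduced.

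**2. Correlation of the two tests.** SAP 2.2 has subjects "randomly allocated in a 1:1:1 ratio to the three treatment groups". Let v be the variance of one arm mean. The covariance of (A − B) and (A − C) is v, and each difference has variance 2v. The correlation is v / 2v = 0.5.

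**3. Family-wise error with both nulls true.** If H2 is tested whatever happens to H1:

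P(at least one rejection) = P(reject H1) + P(reject H2) − P(reject both)

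The joint term comes from the bivariate normal distribution with correlation 0.5.

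| | Fixed sequence | H2 also tested ungated |
|---|---|---|
| Solo-better direction, 0.025 each | 0.025 | 0.025 + 0.025 − 0.0046 = 0.0454 |
| Two-sided, 0.05 each | 0.05 | 0.05 + 0.05 − 0.0093 = 0.0907 |

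A simulation of 400,000 trials with t-tests at 49 per arm gave 0.090 two-sided. H2 was significant while H1 was not in 0.041 of trials, which is the excess over 0.05.

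Protocol 2.1 allows countries without OmniPod to randomise to A and B only. A smaller group C would lower the correlation. The limit for independent tests is 0.0494 in the Solo-better direction and 0.0975 two-sided, so the result is not sensitive to this.

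**4. Other configurations.**
- Only H1 false: the only possible false rejection is of H2, at most 0.05.
- Only H2 false: the only possible false rejection is of H1, at most 0.05.

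The excess arises only when both nulls are true.

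**The case against.** The strongest reply is that the primary family is defined by the fixed sequence, which is stated repeatedly in both documents. If claims rest on that sequence alone, error stays at 5%. No passage gives the secondary tests confirmatory status. Protocol 11.6 leaves details to the SAP, and SAP 6.6 restates the gate. The bullet does not appear in the secondary objectives (Protocol 4.2) or in the SAP's list of additional parameters (SAP 2.1). SAP 6.1 rules out tests that the SAP does not explicitly specify, and 6.8.1.1 names neither OmniPod nor Visit 4. It could be read as covering only the other visits, or as bringing the gate along with the model.

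Most of this stands. A reader might infer that the duplicate in itself undoes the case for no multiplicity correction. The documents do not support that, because someone would first have to use the ungated result for a claim after H1 fails. The absence of a gate in 6.8.1.1 is also read from silence.

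The contradiction remains. Protocol 11.6 has a separate heading for descriptive evaluation, and this bullet is not under it. SAP 6.8.1.2 restates the gate for a secondary endpoint, so its absence one subsection earlier leaves real doubt. SAP 6.1 does not remove that doubt, because 6.8.1.1 does specify an ANCOVA for change scores.

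Both alternative hypotheses favour Solo, so the directional figure is the more relevant one. Although 4.5% lies below 5%, the right comparison is 2.5%, since the plan tests two-sided at 0.05.

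**Conclusion.** The concern holds as a contradiction to be reconciled. One comparison is conditional in Protocol 11.5 and SAP 2.7 and 6.6, unconditional in Protocol 11.6, and unclear in SAP 6.8.1.1.

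The statistical consequence is conditional. If the ungated result supports a claim after H1 fails, and both nulls are true, the chance of a false Solo-better finding rises from 2.5% to about 4.5% (5% to about 9.1% two-sided). The argument in Protocol 11.1 and SAP 2.8 would then no longer apply. These figures assume 1:1:1 allocation and approximately normal test statistics.

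A reader might also infer that the trial needs more subjects. It does not: with the duplicate removed, gated or made descriptive, 49 per group and 60 enrolled stand. The revision history records that hierarchical testing of Solo vs OmniPod was added in version 2.0, so the bullet may be a leftover, but the documents do not say so.

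**What to change.** Add to SAP 6.8.1.1, before Visit 4 results are seen:

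*The Visit 4 comparison of Solo with OmniPod on the DTQ change score is tested only under section 2.7. If the Solo vs MDI null hypothesis is not rejected, this comparison is reported descriptively (estimate and confidence interval), with no confirmatory claim.*

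Delete the duplicate bullet from Protocol 11.6 at the next amendment. Protocol 12.7 requires ethics committee submission for protocol changes. Because 11.6 defers details to the SAP, the SAP sentence is enough until then.

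Timing matters because Protocol 11.9 and SAP 2.11 plan an analysis once all subjects have passed Visit 4 or withdrawn. SAP version 1.2 already describes some final visits in the past tense, and the documents do not say whether Visit 4 results had been seen. If they had, the addition should be dated and reported as made afterwards.

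The cost is one sentence in the SAP and one deletion in the protocol. No subjects are added and no estimate is lost.

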## 11.7 Safety Analysis

All AEs will be coded using the Medical Dictionary for Regulatory Activities (MedDRA). Only AEs occurring after the start of the treatment with either MDI, mylife™ Omnipod® or Accu-Chek® Solo micropump system will be included in the AEs tables.

Summaries of incidence rates (frequencies and percentages) of individual AEs by MedDRA System Organ Class and Preferred Term will be prepared. Such summaries will be displayed for all AEs, AEs by maximum severity, AEs by strongest causality to study device (and any associated pump devices), and AEs leading to withdrawal of study device.

Deaths, other SAEs and AEs leading to withdrawal will be listed separately.

In addition, the sub-group of ADEs and SADEs will also be summarized by MedDRA System Organ Class and Preferred Term including summaries by study device.

Episodes (numbers) of the following AEs will be summarized:

- Symptomatic hypoglycemia
- Severe hypoglycemia (SAEs)
- Diabetic Ketoacidosis (SAEs)

The following ADEs are of particular interest:

- ADEs leading to replacement of device.

Incidence rates of all ADEs and of these ADEs and AEs of special interest (as captured on the AE Form in the eCRF) per 100 patient years will be calculated together with exact two-sided 95% CIs assuming that the number of special AEs observed in the study is Poisson distributed.

### **11.8 Concomitant Medication**

Previous and concomitant medications (separated for diabetes and for other indications) will be listed by subject.

### **11.9 Interim Analysis**

An interim analysis will be conducted when all patients have either passed visit 4 (End of parallel phase) or withdrawn from the study, i.e. when all data for performing the primary analysis and the majority of the secondary analyses will be available. No changes on the study protocol will be made due to the results of this interim analysis.

## **12 Ethical and Legal Considerations**

### **12.1 Statement of Compliance**

The study will be performed in accordance with the principles stated in the World Medical Association's Declaration of Helsinki "Recommendations Guiding Physicians in Biomedical Research Involving Human Subjects" (Fortaleza, 2013), that are consistent with the principles outlined in the ICH Guideline on GCP E6 (R2) (November 9, 2016 where it applies to medical devices and the applicable national regulations for medical device law and applicable ordinances, for the provisions of ISO 14155:2011(E), the European Medical Device Directive (e.g. 93/42/EEC), FDA 21 CFR Parts 11, 50, 54, 56, 99, 312, 803, 812, 814 and 820.30, as applicable in each participating country.

### **12.2 Subject Informed Consent**

It is the responsibility of the Investigator, or a person designated by the Investigator (if acceptable by local regulations), to obtain written Subject informed consent – before any study procedures – from each subject considering participation in this study, after adequate explanation of the aims, methods, anticipated benefits, and potential hazards of the study – orally as well as presented in the written Subject Information Leaflet.

The Investigator or designee (if applicable) must also explain that the subject is completely free to refuse to enter the study or to withdraw from the study at any time, for any reason and could return to standard care.

The Investigator or authorized staff must document the date of each subject's informed consent in the respective eCRF.

Furthermore, in case that Screening and Baseline Visits are combined, the time point of the Subject informed consent must be documented.

If any new safety information results in significant changes in the risk/benefit assessment, the Subject Information Leaflet and/or the Informed Consent Form should be reviewed, updated and re-submitted to the EC/IRB for approval.

Subjects already participating in the study should be informed of the new information, and asked to give their written informed consent to continue in the study.

New subjects shall only receive the updated documents.

All subjects will be given a copy of the signed Subject Informed Consent Form(s).

### **12.3 Confidentiality of Study Documents and Subject Records**

The Investigator must assure that subjects' anonymity will be maintained and that their identities are protected from unauthorized parties. On the eCRFs or other documents submitted to the Sponsor, subjects should not be identified by their names, but by a unique study identification code, i.e. Subject ID (Number).

The Investigator will keep a **Subject Identification Log** linking study identification codes, and subject contact information. The Investigator will maintain these study documents e.g. subjects' written informed consent forms, in strict confidence and as part of the Investigator's Site File.

Any data obtained from subjects participating in the study may be used to build case studies for educational purposes and all identifying data will be completely removed or blacked-out for these purposes.

#### **12.4 Data Protection**

The subject will be informed of his/her right of access, objection and correction of the data recorded during this study, and that this right may be exercised at any time through his/her physician.

Information relating to participating physicians will be declared and the physicians will be informed – within the framework of their agreement – of their right to access, object to and correct this information.

#### **12.5 Independent Ethics Committee**

This protocol and any accompanying material provided to the subject (such as subject information sheets or descriptions of the study used to obtain informed consent) as well as any advertising used or compensation given to the subject, will be submitted by the Sponsor to an EC. Approval from the committee must be obtained before starting the study, and should be documented in a letter to the Sponsor specifying the date on which the committee met and granted the approval. Any modifications made to the protocol after receipt of the EC approval must be re-submitted by the Sponsor to the Committee in accordance with local procedures and regulatory requirements.

When no local committee exists, the Sponsor will submit the protocol to a regional committee. If no regional committee exists, the Sponsor will submit the protocol to the European Ethics Review Committee.

#### **12.6 Regulatory Authorities**

Submissions and/or notification to Regulatory Authorities will be performed as required by local legislation in each participating country for this type of study.

#### **12.7 Amendments to the Clinical Study Protocol**

Study protocol modifications to ongoing studies must be made only after consultation between an appropriate representative of the Sponsor and the Investigator. These modifications must be prepared by a representative of the Sponsor and initially reviewed and approved by the appropriate representatives of the Sponsor and Statistician.

All study protocol modifications must be submitted to the appropriate EC for approval in accordance with local procedures, and Competent/Regulatory Authorities as required. Approval must be granted in writing before any changes can be implemented, except for those changes necessary to eliminate an immediate hazard to the subjects, or when the change(s) involve only logistical or administrative aspects of the study (e.g. change in Monitor, change of telephone number). Note: these changes will be re-submitted for EC/IRB review and approval as soon as possible.

